9.2.1 BIOSPECIMEN EVALUATIONS N/A

9.2.2 SAMPLES FOR GENETIC/GENOMIC ANALYSIS N/A

9.3 SAFETY ASSESSMENTS N/A

Study assessments that will be done to ensure inclusion and exclusion criteria are outlined as part of the inclusion and exclusion criteria in Section 6 (Study Population) and Section 9 (Study Assessments and Procedures).

Baseline suicide-specific measures are reviewed by a member of the study staff to determine if any additional assessment or intervention is warranted.

Safety Assessment Specific to EMA: Participants will be instructed to complete the EMA surveys in a safe place and during a time when they can briefly (< 5 minutes) stop what they are doing to answer the EMA questions. Participants will have up to an hour to respond to the questions to allow them time to respond to the EMA prompts in a safe place.

Risk of suicide might be a concern for some participants. Although suicidal ideation is a risk factor for suicidal behavior, most people who think about suicide do not act on these thoughts. Additionally, studies have demonstrated that repeated assessment does not cause or lead to suicidal thoughts/behaviors. As such, the current protocol itself is not likely to increase participant's risk for suicide. Nonetheless, suicide risk might naturally change throughout the course of the study, and we have developed a detailed protocol to address safety concerns that might arise. For suicidality reported during EMA prompts, our research team has successfully conducted a number of studies assessing suicidality via EMA among high-risk patients, including both adolescents and adults.

The following procedures were developed in collaboration with the National Institute of Mental Health (NIMH) and have been successfully used by our team and collaborators to manage suicide risk identified via EMA. We will not actively monitor EMA data for suicide content for several reasons: 1) Any one instance of elevated suicidal ideation or behavior is unlikely to predict a future death by suicide. Intervention in this context might result in unnecessary psychiatric hospitalization, loss of freedom or employment due to unexcused work absence for our participants, or violation of privacy. In the most extreme of cases, unnecessary intervention can result in physical harm or death to the patient (i.e., combative interactions with first responders). 2) For a small subset of our sample, the presence of suicidal ideation may be frequent and chronic, and reacting to each instance would be clinically counterproductive. 3) As this study is designed in part to identify novel risk factors for suicide, intervention in the presence an instance of elevated suicidal ideation or behavior will alter the nature of the study, making it much more difficult to achieve our study goals.

The need to protect participant safety must be balanced against the statistically unlikely event of a death by suicide, the inherent risk of overreacting and unnecessarily harming or inconveniencing our participants, and the effect of increased contact with participants on study aims. Consequently, all participants will be explicitly instructed during the app training that no one will be monitoring data

Abbreviated Title: mCPT+CRP

Version Date: 07/10/25

collected from the mobile app in real-time and will be provided instead with resources if they indicate suicide risk (threshold criteria described below): National Suicide Prevention Lifeline (Call or Text): 9-8-8); For emergencies, call 9-1-1 and ask for a CIT (Crisis Intervention Team) Officer. All participants are provided with an EMA survey that can be accessed ‘on demand’ that contains a list of mental health resources, including the suicide prevention hotline, should they experience a crisis or desire assistance during periods when they are not responding to EMA prompts.

If, during the course of an EMA survey, a participant “flags” as being at current high risk for suicide, they are directed within the survey to a “we are concerned about you” message. This message will contain information expressing concern about the participant’s wellbeing, remind the participant that EMA responses are not actively monitored by the research team, and provide resources for the participant to reach out to for help (including the suicide prevention hotline and information about nearby emergency resources). The following criteria will be used to flag the “we care are concerned about you” message: Suicidal intent: defined as a score of 3 or higher (range 0-4) on the suicidal intent item, “how sure are you that you want to kill yourself?”; Suicidal Behavior: defined as a positive endorsement of the item, “have you done anything to hurt yourself with at least some intent or desire to die?” or selected any suicide-related behavior from the item, “In the past 2 hours, have you done any of the following.” See Appendices for the EMA MetricWire “we are concerned about you” Message.

All interview measures as well as indicated safety assessments will be performed by qualified personnel.

For this study, all Adverse Events Documents collected on patients for this protocol will be reviewed by the PIs at least monthly to determine if a serious safety problem has emerged that result in a change or early termination of the protocol such as:

- suspending enrollment due to safety or efficacy, or
- termination of the study due to a significant change in risks or benefits.

Any protocol modifications, problematic safety reports, unanticipated problems, and/or suspension or early termination of a study will be reported to all members of the research team, the UTHSCSA IRB, the CRDAMC Human Protections Director, the STRONG STAR Data Safety Monitoring Board (DSMB), the sponsor, and the funder according to each’s policies and guidance. Suspension and early termination of a study will be reported immediately to the STRONG STAR Data Safety Monitoring Board (DSMB), the sponsor, and the funder.

9.4 ADVERSE EVENTS AND SERIOUS ADVERSE EVENTS.

Adverse Event definition: An adverse event (AE) is defined as any untoward or unfavorable medical occurrence in a human subject, including any abnormal sign (e.g., abnormal physical exam or laboratory finding), symptom, or disease, that is a change from baseline, whether or not considered related to the subject’s participation in the research. For this study, all adverse events will be documented at each study visit and be completed with the last study visit. Serious Adverse Event definition: A serious adverse event (SAE) is any adverse event that:

1. results in death;
2. is life-threatening (places the subject at immediate risk of death from the event as it occurred);
3. results in inpatient hospitalization or prolongation of existing hospitalization;
4. results in a persistent or significant disability/incapacity;
5. results in a congenital anomaly/birth defect; or
6. based upon appropriate medical judgment, may jeopardize the subject’s health and may require medical or surgical intervention to prevent one of the other outcomes listed in this definition.

9.5 UNANTICIPATED PROBLEMS

Abbreviated Title: mCPT+CRP

Version Date: 07/10/25

Unanticipated Problem Involving Risks to Subjects or Others definition: Unanticipated problem involving risk to subjects or others includes any incident, experience or outcome that meets all of the following criteria:

- A. unexpected (in terms of nature, severity, or frequency) given (a) the research procedures that are described in the protocol-related documents, such as the IRB-approved research protocol and informed consent document; and (b) the characteristics of the subject population being studied; and
- B. definitely related or probably related to participation in the research; and
- C. suggests that the research places subjects or others at a greater risk of harm (including physical, psychological, economic, or social harm) than was previously known or recognized.

9.6 REPORTING OF PREGNANCY

N/A

10. STATISTICAL CONSIDERATIONS

10.1 STATISTICAL HYPOTHESIS

Aim 1: Determine if the addition of CRP to CPT reduces suicide attempts.

Hypothesis 1 (H1): The rate of follow-up suicidal behavior will be significantly reduced among military personnel receiving CRP versus usual care risk management in addition to massed CPT.

Hypothesis 2 (H2): Reductions in the severity of suicidal ideation will be significantly larger among military personnel receiving CRP versus usual care risk management.

Aim 2: Identify early markers of treatment response and relapse of suicide risk.

Hypothesis 3 (H3): Less severe suicide risk features during treatment will predict treatment response (i.e., change in severity of suicidal ideation) and treatment relapse (i.e., follow-up suicidal behavior). Exploratory Research Question 1 (RQ1): Which subjective, objective, and treatment-related factors are most useful for predicting treatment response (i.e., change in severity of suicidal ideation) and treatment relapse (i.e., follow-up suicidal behavior)?

Aim 3: Identify treatment content and design features that influence treatment effectiveness and acceptability.

Hypothesis 4 (H4): More frequent CRP use will be correlated with reductions in suicide attempts and suicidal ideation. Exploratory RQ2: Which treatment components and design features do participants find most helpful for reducing suicidal ideation and attempts?

10.2 SAMPLE SIZE DETERMINATION

See Power and sample size calculations in Section 10.4.2 (Analysis of the Primary Endpoints) below.

10.3 POPULATIONS FOR ANALYSES

Data collected from all participants will be included for analysis. Comparisons will be made to determine differences in outcome measures between the intervention groups.

10.4 STATISTICAL ANALYSES

10.4.1 General Approach

Prior to statistical analyses, data will be screened to assess the need for scale transformations (e.g., log, reciprocal) to normalize distributions or reduce variance heterogeneity. The study design is a two-arm randomized clinical trial with a superiority hypothesis (i.e., CRP superior to usual care). Analyses will use survival analysis and mixed effects regression with repeated measures. Follow-up assessment data will be collected from participants even if they drop out of therapy early. The primary focus will be on

Abbreviated Title: mCPT+CRP

Version Date: 07/10/25

group differences over time. All hypotheses will be two-sided at the $\alpha=.05$ level. Little's MCAR test will be used to determine if data are missing at random (Li, 2013; Little et al., 2002) and random effects pattern-mixture modeling will be used to determine if missingness influences longitudinal results (Hedeker & Gibbons, 1997; Little, 1993). The principal statistical software to be used is SAS 9.4 supplemented with SPSS, R, and MPlus.

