Cognitive processing therapy for PTSD rapidly reduces suicidal ideation. Another research gap identified by the PHCoE is the need for additional research focused on how diagnosis-specific therapies and interventions may—or may not—reduce suicidal thoughts and behaviors. Research by our team and others suggests PTSD treatments are associated with significant reductions in suicidal ideation (Brown et al., 2019, 2020; [name] et al., 2016, 2018, 2022; Gradus et al., 2013). PTSD is a common mental health condition among U.S. military personnel (Tanielian et al., 2008) and significant risk factor for suicide. PTSD is not just a consequence of military service, however; sexual assault, domestic abuse, accidents, and child abuse are other common contributors to PTSD. PTSD significantly increases the risk of suicidal thoughts, behaviors, and death (May & Klonsky, 2016; Nock et al., 2009; 2018) and is one of the few psychiatric conditions that distinguishes people who have attempted suicide from those who only thought about suicide, suggesting PTSD facilitates the transition from suicidal thought to action (Nock et al., 2009; May & Klonsky, 2016). Early treatment of PTSD could therefore reduce suicide risk in the military. Cognitive processing therapy (CPT) is a trauma-focused therapy that produces very large reductions in PTSD symptoms (Forbes et al., 2010; Watts et al., 2013) and suicidal ideation ([name] et al., 2016; Gradus et al., 2013; Resick et al., 2017). PI [name] has further shown that CPT's effects on reducing suicidal ideation are accelerated when CPT sessions are scheduled daily over 2 weeks (called “massed” CPT) versus the more typical pace of scheduling sessions weekly over several months ([name] et al., 2018; Sciarrino et al., 2020). Massed CPT therefore achieves similar reductions in suicidal ideation and PTSD symptoms within a much shorter timeframe. Conclusions about CPT's effects on suicidal *behavior* remain unknown, however, because studies to date have excluded higher risk patients and/or did not enroll a large enough number of high-risk patients to examine suicidal behavior as an outcome. To address this critical knowledge gap, the proposed study will: (a) enroll only high-risk patients who report active suicidal ideation or a recent suicide attempt and (b) examine suicidal behavior as our primary outcome.

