4.3 JUSTIFICATION FOR INTERVENTION

CRP accelerates reductions in suicidal ideation and prevents suicidal behaviors when used in conjunction with CPT.

Preliminary data from a pilot RCT conducted by PI [name] suggests the addition of CRP to massed CPT leads to (a) faster and larger reductions in suicidal ideation among military personnel and veterans diagnosed with PTSD or subthreshold PTSD (i.e., meeting 3 of 4 diagnostic criteria) and (b) reduces suicide attempts during follow-up. In that study, 74 military personnel and veterans reporting active suicidal ideation within the past week were randomly assigned to receive massed CPT in conjunction with either CRP or usual care suicide risk management procedures (e.g., suicide risk screening, safety planning). As compared to usual care (n = 33), participants

Figure 2. Mean suicidal ideation (log-transformed) among military personnel and veterans randomized to CRP (red) or safety planning (blue) during massed CPT for PTSD

Abbreviated Title: mCPT+CRP

Version Date: 07/10/25

receiving CRP (n = 41) reported significantly larger reductions in suicidal ideation within 1 week ($t(281) = 2.1$, $p = .041$; see Figure 2), which corresponds to the midpoint of massed CPT. By 6 months, there were 73.2% fewer suicide attempts in the CRP group (7 attempts) versus usual care (21 attempts), suggesting CRP also reduced suicidal behaviors. These pilot results support the feasibility of our proposed study and suggest CRP may be more effective than usual care suicide risk management strategies for rapidly reducing suicide risk among military personnel with PTSD. Though promising, these findings require further examination in a larger clinical trial with suicidal behavior as the primary outcome.

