10.4.2 Analysis of the Primary Endpoints

Hypothesis 1: The rate of follow-up suicidal behavior will be significantly reduced among military personnel receiving CRP versus usual care risk management in addition to massed CPT.

Survival analysis with time-to-suicide attempt will be used to test overall differences between the two intervention groups. We will use the hazard ratio derived from the Cox regression supplemented with the log-rank and Wilcoxon statistics derived from the Kaplan-Meier method. Time will be calculated as number of days since the intake appointment. Multiple suicide attempts within participants will be handled using the Andersen-Gill counting process model (Anderson & Gill, 1982), which assumes that the time increments between multiple suicide attempts can be explained by past suicide attempts (e.g., shorter time intervals between suicide attempts are more likely among patients who have previously attempted suicide). **Power Analysis:** Power calculations for H1 were conducted using PROC POWER in the SAS 9.4 software. Anticipated suicide attempt rates were based on previously published clinical trials conducted within and external to the military. In previous studies of cognitive behavioral therapies for suicide prevention, the suicide attempt rate in the usual care conditions often ranges from 40-50% during the first year and active suicide-focused interventions typically have 50% lower suicide attempt rates (Brown et al., 2005; Gysin-Maillart et al., 2016; Linehan et al., 1991; Rudd et al., 2015). In our previous RCT of CRP versus usual care ([name] et al., 2017), participants receiving CRP were 76% less likely to attempt suicide. Results of our pilot study of massed CPT yielded a similar 73% reduction in suicide attempts in the CRP group versus usual care. We therefore estimated statistical power for hazard ratios ranging from 0.50-0.75 when suicide attempt rates in usual care ranged from 30-50%, assuming 15% attrition, 1-year follow-up, and a two-tailed $p<.05$. $N=150$ yielded $>80\%$ power under nearly all conditions.

Hypothesis 2: Reductions in the severity of suicidal ideation will be significantly larger among military personnel receiving CRP versus usual care risk management.

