Mixed effects regression models with repeated measures will be used to test group differences in suicidal ideation over time. Treatment group, time, and the treatment*time interaction will be entered as independent variables and SSI scores as the outcome. Random intercepts and slopes will be tested, and covariance structures will be selected by comparison of likelihood criteria (e.g., Akaike's Information Criteria). Group differences in mean SSI scores will be probed at 2, 4, 13, 26, 39, and 52 weeks, with the largest differences between groups expected to occur at 2 and 4 weeks. Consistent with these expectations, we will also compare the SSI slopes from baseline to session 5 (treatment midpoint) and session 10 (treatment end) to determine if the rate of change in suicidal ideation differs across groups.

Power Analysis: We used the General Linear Mixed Model Power and Sample Size (GLIMMPS) software to calculate power for H2 using data from our pilot study to estimate SSI mean differences between groups at baseline ($M_{diff}=0$), treatment midpoint ($M_{diff}=4$), and treatment end ($M_{diff}=2$) assuming a two-tailed $p<.05$. Results indicated $N=150$ provided 81% power.

Hypothesis 3: Less severe suicide risk features during treatment will predict treatment response (i.e., change in severity of suicidal ideation) and treatment relapse (i.e., follow-up suicidal behavior).

For H3, we will use suicidal ideation EMA ratings collected during the 2 weeks of massed CPT. We will first calculate the following indices of change in suicidal ideation during the entire 2-week observation

Abbreviated Title: mCPT+CRP

Version Date: 07/10/25

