10.4.3 Analysis of the Secondary Endpoint(s)

See Section 10.4.2 (Analysis of the Primary Endpoints) for the analysis plan for each of the study aims.

Abbreviated Title: mCPT+CRP

Version Date: 07/10/25

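### The protocol names one primary outcome, suicidal behavior, but places H1 to H4 together in its primary-endpoint section at .05 each and names no secondary endpoint

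*Protocol*

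**What the plan says.** On what is primary, the protocol speaks in two ways.

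- **One primary outcome.** Section 2.1 says the study will "examine suicidal behavior as our primary outcome", and Section 4.3 calls for "a larger clinical trial with suicidal behavior as the primary outcome". Section 3 states the primary objective in terms of suicidal behaviors and does not mention ideation.
- **Several primary endpoints.** Under the heading "10.4.2 Analysis of the Primary Endpoints" stand H1 (suicidal behavior), H2 (ideation on the SSI), H3, H4 and both exploratory research questions. Section 10.4.3, meant for secondary endpoints, names none and reads: "See Section 10.4.2 (Analysis of the Primary Endpoints) for the analysis plan for each of the study aims".

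On the error level, Section 10.4.1 says "All hypotheses will be two-sided at the" .05 level. Section 10.4.2 then powers H1 and H2 separately, each at the full two-tailed .05.

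Aim 1 covers both hypotheses but is worded for one of them: "Aim 1: Determine if the addition of CRP to CPT reduces suicide attempts". Within H1, the Cox hazard ratio is to be "supplemented with the log-rank and Wilcoxon statistics derived from the Kaplan-Meier method", and repeat attempts are to be handled by an Andersen-Gill model. Within H2, a treatment-by-time mixed model comes first. Then "Group differences in mean SSI scores will be probed at 2, 4, 13, 26, 39, and 52 weeks", and two early slopes are compared as well.

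**The concern.** A reader who starts from Sections 2.1, 3 and 4.3 expects the trial to stand or fall on suicide attempts. A reader who starts from Section 10.4 finds ideation with the same primary label and the same .05. Nothing in the document says which account governs the report.

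The stake is the claim made at the end. If attempts do not differ between arms and ideation does, Section 10.4.2 lets the ideation result be described as a primary endpoint that was met. That is a weaker claim than the one the trial was set up to test, and its error rate is not the stated 5% if success on either hypothesis is enough.

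**Working it through.** **Inputs**

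- α = .05 two-sided for each hypothesis (Section 10.4.1).
- Two lead tests under Aim 1: the hazard ratio for H1 and the treatment-by-time test for H2 (Section 10.4.2).
- N = 150, 15% attrition, hazard ratios from 0.50, usual-care attempt rates of 30 to 50%, and a stated 81% power for H2 (Section 10.4.2).
- Equal arms are assumed, from the allocation method in Section 7.3.

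**Step 1: the stated level.** One lead test gives 1 − 0.95 = 5%. This reproduces the protocol's figure, provided H1 alone decides.

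**Step 2: either lead test counts.** With two independent tests the error is 1 − (1 − .05)² = 1 − 0.9025 = 9.75%. The protocol gives no correlation between the two test statistics, so bounds are useful. The error is 5% if they always agree and at most .05 + .05 = 10% under any dependence.

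**Step 3: can a split result easily happen?** Suppose CRP changes ideation by as much as the H2 power calculation assumes but leaves attempts unchanged. Taking the stated 81% at face value (no SD or correlation is given, so it cannot be checked) and the tests as independent, H2 is significant and H1 is not in about 0.95 × 0.81 = 77% of trials. A split result is then the expected one, so its label matters.

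**Step 4: what each repair does to H1.** The expected number of events is D = (N/2) × [p + 1 − (1 − p)^HR] with N = 150 × 0.85 = 127.5. Power is Φ(½√D × |ln HR| − z), by Schoenfeld's formula. At HR 0.50:

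| Usual-care rate p | D | Power at .05 (z = 1.96) | Power at .025 (z = 2.24) |
|---|---|---|---|
| 30% | 29.5 | 47% | 36% |
| 40% | 39.9 | 59% | 48% |
| 50% | 50.5 | 69% | 59% |

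These powers fall short of the protocol's claim of more than 80% under nearly all conditions. That is a separate matter; they serve here only to compare repairs. Making H1 the sole primary test keeps the primary claim at 5% and leaves H1's power untouched. Keeping H1 and H2 as co-primary with a Bonferroni split would cost H1 10 to 11 percentage points.

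**The case against.** The best defence is that the heading of Section 10.4.2 reflects a template and not a classification. Two research questions that the protocol itself calls exploratory sit under it, so placement there cannot by itself confer primary status. The sentence in Section 10.4.3 also appears unchanged under sub-group analyses (Section 10.4.6), where it merely points to where the methods are described. A testing order or alpha allocation is commonly left to a SAP, which is not at hand, so its absence is no fault.

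Much of this stands. It makes careless placement the likely cause and limits the point to what the protocol states. It does not remove the conflict: the only section on secondary endpoints names none, and H1 and H2 are each powered at the full .05. A SAP that made H2 secondary would have to depart from the protocol's own heading.

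A reader might go further and infer that Aim 1 could be declared met on any of about a dozen tests. The count is right: three or four statistics for H1, depending on whether Andersen-Gill is a separate model, plus 1 + 6 + 2 = 9 for H2. Simulation under assumed correlations puts the chance of at least one false positive among them at about 30 to 34%. The documents do not support that reading. No passage says any single test suffices. Aim 1 is worded for attempts, while nine of the tests concern ideation. Log-rank and Wilcoxon only supplement the Cox hazard ratio, and the visit contrasts are described as probes. H3 and H4 belong to Aims 2 and 3 and add nothing to Aim 1, so a four-hypothesis figure of 1 − 0.95⁴ = 18.5% does not apply to it either.

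**Conclusion.** The protocol contradicts itself on what is primary, and this should be corrected. The defensible size is 9.75% in place of 5%. It rests on two conditions: that success on either lead test under Aim 1 would be taken as success, which the protocol neither states nor rules out, and that the two tests are independent. Positive dependence between ideation and attempts would bring the figure down towards 5%. If H1 alone decides, as Sections 2.1, 3 and 4.3 imply, the error is 5% and only the labels are wrong. The practical risk is therefore a misdescribed result, not a faulty test.

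**What to change.** Bring Sections 10.4.2 and 10.4.3 into line with Sections 2.1, 3 and 4.3:

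- **Primary.** H1 is the sole primary hypothesis, judged at two-sided .05 on one named treatment hazard ratio. Say whether it comes from the Cox model for time to first attempt or from the Andersen-Gill model. The other model, log-rank and Wilcoxon are supportive.
- **Secondary.** H2 moves to Section 10.4.3 with one named lead contrast. The remaining visit and slope contrasts are descriptive.
- **Other.** H3, H4 and the two research questions leave the primary section.

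Testing H2 only if H1 is significant is optional. With the H1 powers shown above, that rule would often prevent a confirmatory test of H2, and it is not needed to resolve the contradiction.

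The cost is a paragraph of wording, with no change to sample size or data collection. The downside is that a positive H2 alone can no longer be reported as a positive primary result.
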